7.1. General

The Cytosponge[™] Cell Collection Device (Cytosponge) is intended to collect surface cells from the esophagus. The device consists of a swallowable capsule, which dissolves in the body cavity, releasing a self-expandable sponge. The sponge is then retrieved from the esophagus using an attached string. During the retrieval process, the sponge collects cells from the most superficial layer of the esophageal mucosa. Once removed from the patient, the sponge and cells are retained for investigation and/or testing.

The Cytosponge[™] Cell Collection Device (Cytosponge) received 510(k) clearance from the FDA on November 26, 2014 (K142695). The Cytosponge [™] Cell Collection device is a Class II product under 21 CFR 874.4710 esophagoscope (flexible or rigid) and accessories. The sponsor has determined clinical study COVB2710467 entitled - Assessment Of A Minimally Invasive Esophageal Cytology Collection System In Patients With Barrett's Esophagus Or GERD Symptoms is a Non-Significant Risk (NSR) Device study based on "Information Sheet Guidance for IRBs, Clinical Investigators, and Sponsors – Significant Risk and Non-significant Risk Medical Device Studies" published by the FDA (January 2006).

Version G 01-DEC-2017

7.2 Dosage Form and Route of Administration

Figure 2: Cytosponge with planned packaging and retrieval cord

Figure 3: Cytosponge I

The Cytosponge[™] device (referred to hereafter as the "Cytosponge") will be supplied by Medtronic to the participating sites. Study sites will be responsible for storage and accountability of the device. The Cytosponge lifetime/use by date will be confirmed on the product packaging. The device received FDA 510(k) clearance on November 26, 2014 (K142695).

Cytosponge administration will occur after an overnight fast to minimize the possibility of aspiration of any gastric contents. Every administered sponge will be assessed post-procedure for signs of fracture or incomplete retrieval of the sponge. Subjects will undergo administration of the Cytosponge[™] according to the IFU. Briefly, subjects will be placed in the seated position and will swallow the capsule with 150 – 250 mL of water. Additional water may be used if necessary. The sponge is attached to a length of suture material which passes out through the capsule. The suture is affixed to a retainer card which is held by the subject or administrator to prevent inadvertent swallowing of the suture. The string is to be held without tension as peristalsis and gravity advance the capsule into the stomach.

The capsule dissolves in the stomach, allowing the sponge to expand to its full size. Seven minutes and 30 seconds to ten minutes after ingestion, the sponge is then withdrawn by gentle traction on the suture, collecting cells from the lining of the esophagus in passing.

After retrieval, the string is cut and the retrieved foam sphere containing the cytological specimen is immersed in fixative and stored refrigerated (1° to $12^{\circ}C$ [34° to $54^{\circ}F$]) until shipped. Samples will be

COVB2710467

Version G 01-DEC-2017

shipped to an accredited pathology laboratory for processing.

In the unlikely case of incomplete retrieval or sponge detachment, the sponge will be retrieved with a Roth net at the standard of care endoscopy which will routinely immediately follow the administration of the sponge per the study protocol. Any bleeding noted, either clinically following the sponge administration or due to blood on the sponge itself, will be similarly investigated, and, as necessary, treated during the subsequent endoscopy. Because study inclusion/exclusion criteria are designed to exclude those at highest risk for a bleeding complication, the risk of bleeding in this study should be extremely low.

If a subject fails to swallow the Cytosponge, the subject will be asked to swallow again. Subjects who are willing to try again will be asked to wait 5 minutes before the Cytosponge is presented to them again. Subjects will be able to try up to two times before they are classified as "Cytosponge swallowing failure" and discontinued by the investigator.

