6.1. Duration

Participation in the study may last about4-10 days after the procedure. Subjects will be contacted 7 days (+/- 3 days) following the Cytosponge and upper endoscopy procedures. During this phone call, adverse events will be assessed and subjects will complete final questionnaire. Participation in the study is complete when subjects have completed the follow-up phone call.

If the Cytosponge tissue specimen is reported as inadequate by the central pathologist, the subject will be asked to return for repeat Cytosponge administration. Only the Cytosponge[™] Cell Collection capsule administration will be repeated. Questionnaires and the endoscopy procedure will not be repeated.

The study is expected to last a total of 24 months (2 years).

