9.1. Schedule of Events

Assessment	Screening/Enrollment Visit	Follow-Up Phone Call (7 days +/- 3 days after Enrollment)	Repeat Cytosponge
Informed Consent Form	х		
Demographics	X		
Medical History	X		
Inclusion/Exclusion Criteria	x		
Cytosponge Administration	x		\mathbf{X}^1
Visual Analog Scale	X ²		
Routine Care Endoscopy with Biopsy	X ^{3,4}		
Impact of Event Scale		X	
Procedure Preference and Acceptability Questionnaire		x	
Adverse Events ⁵	Х	X	Х

¹If the initial Cytosponge sample is inadequate, sites will be notified and subjects will be asked to return for repeat Cytosponge administration. Only the Cytosponge administration will be repeated. Questionnaires and the endoscopy procedure will not be repeated on these patients.

²VAS should be administered immediately following completion of the Cytosponge and prior to the upper endoscopy.

COVB2710467

Version G 01-DEC-2017

³Routine care biopsies should be taken during the endoscopy following the Cytosponge as this is considered standard of care for the target population.

⁴For subjects presenting for GERD, a single set of 4 quadrant biopsies (4 pieces of tissue total) of the gastric cardia (TGF+1) should be taken for this research study. The research specific biopsies will be taken in addition to any routine care biopsies taken during the procedure and will still be obtained even if routine care biopsies are not taken. The Sponsor will pay for any charges related to collection and pathology of the research specific gastric cardia biopsies.

It is encouraged for Investigators to take photos of the gastroesophageal junction (GEJ) during the endoscopy procedure.

⁵Every adverse event must be reported to the sponsor and recorded in the electronic case report form. Sites are responsible for following local IRB guidelines for reporting adverse events to their local IRB.

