10.1. Potential Risks

There are several possible risks that could occur when swallowing the Cytosponge capsule which include but are not limited to:

- Aspiration (accidentally inhaling material from the stomach into the lungs) and/or airway obstruction are possibilities but these risks are expected to be minimal.
- Although the sponge is soft, possible risks include, bleeding, pain, vomiting, sore/irritated throat, and burning sensation from any mucosal surfaces of the mouth, stomach or esophagus (swallowing tube) which comes in contact with the sponge.
- Laceration of any mucosal surface coming into contact with the sponge is possible, including mucosal surfaces of the stomach, esophagus, throat or mouth. Although very unlikely, perforation of the stomach or esophagus is also possible which could require secondary intervention.
- Although the risk has been found to be 2%, sponge detachment from the suture could also occur. Should this occur, the sponge will be retrieved during the planned endoscopy that follows administration of the sponge. Although not observed in previous Cytosponge studies the risk of infection or intestinal obstruction is a possibility.

The current study has been designed to minimize occurrence of these potential risks by use of the exclusion criteria. Most subjects enrolled in this study will have previously received an upper endoscopy, which will document the absence of esophageal varices and strictures. During administration of the sponge, the patient is not sedated and the device does not render the upper esophageal sphincter incompetent. These elements further reduce the overall risk for serious adverse events.

All serious adverse events, which, based on the investigator's judgment, are considered to be device related, should be reported to Medtronic-GI Solutions within 24 hours after the investigator is made aware of the event.

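### A repeat sponge has no planned endoscopy to retrieve a detached sponge or treat bleeding, and no scheduled adverse-event call afterwards

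*Protocol*

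**What the plan says.** **Retrieval and bleeding.** Protocol 7.2 says of every administration: "Every administered sponge will be assessed post-procedure for signs of fracture or incomplete retrieval of the sponge". If the sponge detaches or is not fully retrieved, "the sponge will be retrieved with a Roth net at the standard of care endoscopy which will routinely immediately follow the administration". Any bleeding "will be similarly investigated, and, as necessary, treated during the subsequent endoscopy". Section 10.1 gives the size of the detachment risk, "Although the risk has been found to be 2%, sponge detachment from the suture could also occur", and the same remedy: "the sponge will be retrieved during the planned endoscopy that follows administration of the sponge".

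**Repeat sponge.** Section 6.1 says: "If the Cytosponge tissue specimen is reported as inadequate by the central pathologist, the subject will be asked to return for repeat Cytosponge administration". It then says: "Questionnaires and the endoscopy procedure will not be repeated". Footnote 1 to the schedule in 9.1 agrees: "Only the Cytosponge administration will be repeated. Questionnaires and the endoscopy procedure will not be repeated on these patients". The Repeat Cytosponge column of that schedule marks sponge administration and adverse events, and nothing else.

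**Follow-up.** Section 11.1 runs adverse-event collection to the 7-day call after the final sponge, and section 6 times the call from Cytosponge administration. The schedule in 9.1 has a single call, 7 days (+/-3) after enrollment. Section 6.1 puts participation at about 4 to 10 days and ends it at that call. SAP 6.1.1 plans one follow-up only.

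**Analysis.** Protocol section 13 bases the sensitivity estimate from TFF3 data on individuals with an adequate sample and an endoscopy within 48 hours of the sponge. The SAP states that it is based on version G. Its default in 6.1.3 is all available data, and its text on secondary objective 1 sets no time limit. SAP 6.6.1.1.1 places the repeat sponge at 30 days (+/-10). Protocol version G sets no repeat window.

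**The concern.** The stated response to a detached sponge or a bleed is an endoscopy that already follows on the same day. That holds for the first sponge. At a repeat there is no such endoscopy, so the risk text describes a safeguard that these subjects do not have as part of the plan. A detachment or a significant bleed would need an unplanned procedure.

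The follow-up gap bears on the same subjects. A site working from the 9.1 schedule could regard a subject as finished at the day 4 to 10 call, give a repeat later, and make no further call. Delayed events after the second sponge could then go unrecorded, although safety is secondary objective 5.

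The SAP point is smaller. A repeat sample compared with the first visit's endoscopy may fall outside the 48-hour limit, and an analyst who reads only the SAP would not know that a limit exists.

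**Working it through.** **1. Is there a rescue at the repeat visit?** Two measures in the plan reach that visit: inspection of every sponge (7.2) and the adverse-event check (9.1). Both can detect a problem. Neither retrieves a sponge or stops bleeding. The measure that does, the endoscopy, is ruled out at the repeat by 6.1 and 9.1. No other section of the protocol or SAP names a substitute.

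**2. Scale of the detachment risk.** The plan uses the probability of at least one event for its safety statements, so that calculation was reproduced first, with P = 1 - (1 - p)^n:
- Protocol 13: n = 50, p = 5%: 1 - 0.95^50 = 92.3% (stated as above 90%).
- SAP 5: n = 275, p = 1%: 1 - 0.99^275 = 93.7% (stated as above 93%).

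Both agree. The same formula was then applied to repeats. The inputs are p = 2% from 10.1, assumed to hold per administration, and half of it (1%) as a lower case. The documents give no repeat rate, so n is illustrative. Each 1% of 275 subjects recalled adds 275 x 0.01 = 2.75 repeats.

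| Repeats n | Share of 275 | Expected detachments at 2% | P(at least one), 2% | P(at least one), 1% |
|---|---|---|---|---|
| 10 | 3.6% | 0.2 | 1 - 0.98^10 = 18% | 1 - 0.99^10 = 10% |
| 25 | 9.1% | 0.5 | 1 - 0.98^25 = 40% | 1 - 0.99^25 = 22% |
| 50 | 18.2% | 1.0 | 1 - 0.98^50 = 64% | 1 - 0.99^50 = 39% |

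These count detachments without a planned endoscopy, not injuries.

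**3. Is there a call after the repeat?** Section 11.1, and on one reading section 6, require it. The schedule in 9.1, the end of participation in 6.1 and SAP 6.1.1 provide one call only, and 9.1 ties it to enrollment. Taking enrollment and first sponge as day 0, the call falls on days 4 to 10. Under the SAP window the repeat falls on days 20 to 40, so the call precedes it by 20 - 10 = 10 to 40 - 4 = 36 days. Version G sets no window, so under the protocol alone the order is not fixed.

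**4. Does the SAP carry the 48-hour rule?** No. Neither its analysis sets (6.1.3) nor its text on secondary objectives 1 to 3 contains it. Under the SAP's own window a repeat comes 20 x 24 = 480 to 40 x 24 = 960 hours after the first-visit endoscopy, so every repeat sample would miss the limit. Those hours describe the SAP window only, not version G.

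**The case against.** The best reply is that repeat subjects are asked to return after the site is notified. The natural reading is the enrolling site, which stores the devices, has trained staff and performed the endoscopy; section 13 describes the centers as tertiary. Urgent endoscopy is then probably available. Repeat subjects have also just been endoscoped, so varices or a stricture would normally have been seen. Section 10.3 reports that risks including secondary intervention and minor bleeding were reduced to an acceptable level, and the device is cleared. The IFU and the training plan are not available to us and may cover retrieval.

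Most of this stands. A reader might infer that repeat subjects have no access to rescue; the documents do not support that. What remains is that cover is likely but not required, and that the protocol's own retrieval text does not fit the repeat visit.

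On follow-up, a reader might infer that adverse events after a repeat are not collected. That is too strong: 9.1 marks them at the repeat visit, 9.8.1 asks at visits and telephone contacts, and 11.1 intends the later call. The gap is that no schedule contains that call.

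On analysis, a reader might infer that section 13 already bars late repeat samples from all of secondary objective 1, or that including them biases sensitivity. Neither is established. The rule is worded per individual, so a subject with a same-day first sponge and endoscopy arguably meets it even if the adequate sample came later. It is also written for sensitivity only. Section 4.2 describes BE as lifelong barring intervention, so a few weeks may matter little in subjects who are not ablated.

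**Conclusion.** The point holds and should be fixed. The written response to detachment and bleeding depends on an endoscopy that the repeat visit excludes, and the adverse-event call that 11.1 assumes after a repeat is not in any schedule. Both are gaps in what the plan requires; neither shows that sites would act unsafely.

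The size cannot be fixed from the documents. If 2% applies per administration, one detachment is expected per 50 repeats. The probabilities in the table rest on that assumption and on assumed repeat counts.

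The missing 48-hour rule and the leftover repeat window are a secondary inconsistency between SAP and protocol. No effect on sensitivity is claimed. Confidence is medium, mainly because the IFU and training plan were not available.

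**What to change.** 1. In protocol 7.2 and 10.1, state that a repeat sponge has no planned endoscopy and is given only where urgent endoscopic retrieval and bleeding control are available.
2. In 6.1, 9.1 and SAP 6.1.1, add an adverse-event call 7 days (+/-3) after any repeat sponge, and end participation at the last call. This brings them into line with 11.1.
3. In the SAP, carry over the 48-hour rule for TFF3 sensitivity against the study endoscopy, and say that it applies to the sponge sample analysed. Using the same set for specificity, predictive values and accuracy is a proposal, not something the protocol now requires. Delete the 30 (+/-10) day window.

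The adequacy endpoint, after up to two administrations, is unchanged.

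The cost is wording in both documents and one phone call per repeat subject. Limiting where repeats are given is probably a small burden at tertiary centers. Late repeat samples would not count in the sensitivity estimate, so subjects whose only adequate sample is a late repeat would drop out of it.

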7.3 Manufacturer

The product is manufactured at a Medtronic facility located in Sunnyvale, California.

7.4. Packaging

The subject device the Cytosponge[™] Cell Collection Device is a sterile single-use device. The Cytosponge[™] Cell Collection Device consists of a clear, size 00 vegetable-material-derived capsule, which holds a 30mm spherical sponge inside of the capsule. The capsule containing the sponge is attached to silicone-coated braided polyester suture. The suture is attached and secured to a retainer card via an ABS plug. These materials are packaged inside a foil and polyethylene pouch. The product label is applied to the pouch and provides text containing the manufacturing lot and expiration date.

7.5. Intended Population

The intended population consists of people who are having an endoscopic exam to examine their esophagus, stomach, and first part of the small bowel and because the subject has suffered from GERD symptoms at least on a monthly basis for at least 6 months or patients who have been diagnosed with Barrett's esophagus.

COVB2710467

Version G 01-DEC-2017

7.6. Equipment

N/A

7.7. Product Use

Refer to CytoKit IFU_717-0075-01(A) for product use information.

7.8. Product Training Requirements

Each Investigator participating in the clinical trial and the associated clinical study staff will receive training on the clinical protocol, as well as hands-on training in the use of Cytosponge[™] Cell Collection Device and training on Visual Analog Scale. The CASE II Clinical Study Training Plan describes in detail study training requirements.

Sites are required to receive standardized training on Cytosponge administration before enrolling their first study subject. This will require recruiting and enrolling a cohort of healthy volunteers for training purposes. Participants enrolled for training purposes will not count toward enrollment on the study but should be approved by the site's IRBs. Prior to the recruitment of healthy volunteers, sites must receive explicit permission from the sponsor. See Appendix III: Sample Healthy Volunteer ICF.

7.9. Product Receipt and Tracking

Product information will be recorded in the packing slip, Kit Receiving and Disposition Log, and Device Accountability Log. These documents will be kept at the site and a copy will be sent to the sponsor to save in Trial Master Files.

The packing slip will contain the kit and capsule lot numbers, kit and capsule expiration dates, date of order, and date of receipt. The site will confirm sponsor to confirm receipt of the product.

7.10. Product Storage

The device will be labeled CytoKit-R (Research Use Only) and should be stored in a secure (locked) area under the appropriate storage conditions. Access should be limited to designated study staff only. Refer to CytoKit IFU_717-0075-01(A) for appropriate storage condition information.

7.11. Product Return

For all product returns not pertaining to a complaint, a Return Form is to be completed and the product is to be returned to the sponsor. For products being returned due to a complaint, Post-Market Vigilance

CASE II Clinical Investigation Plan					
COVB2710467	Version G 01-DEC-201	7 Page	23 of 61		Medtronic

will provide a complaint number that will be included in the Return Form and shipping label. Expired products can either disposed of or returned to the study sponsor.

7.12. Product Accountability

The Kit Receiving and Disposition Log includes all information within the packing slip, as well as device condition, subject number, and the date the device was used. A copy of this log will be sent to the sponsor after every monitoring visit.

A Device Accountability Log will be sent to the sponsor after a device is used or after the next monitoring visit. It will include the date of the procedure, the device and capsule lot numbers, and the subject number.

8. Selection of Subjects

8.1. Study Population

The study population includes patients with:

- Previous confirmed diagnosis of BE with intestinal metaplasia
- Self-reported heartburn or regurgitation on at least a monthly basis for at least 6 months (GERD arm)
- Prague classification of at least one circumferential centimeter of BE or a total BE segment length of at least 3 centimeters (C1 or CXM3+) (BE arm) (refer to section 9.3)

8.2. Subject Enrollment

Potential subjects will be identified during their GI clinic or procedure visits at their treating institutions. All subjects will be screened and enrolled using ethics committee (EC) / Institutional Review Board (IRB)approved and HIPAA compliant methods.

An investigator, study coordinator, or other qualified personnel will obtain consent prior to any study procedures. Potential subjects will have an opportunity to carefully review the consent form. The details of the study will be reviewed verbally, and all questions will be answered to the satisfaction of the patient. Only adults with the ability to consent will be eligible for enrollment in this study. After the subject signs the consent, a copy of the signed consent will be provided to the subject. Once written consent has been obtained, the coordinator will collect demographic and historical information from the subject pertaining to history of BE and GERD.

COVB2710467

The consent process will be documented by the coordinator in the subject's study file.

8.3. Inclusion Criteria

- 1) Male or female subjects, age 18 and above.
- 2) Able to read, comprehend, and complete the consent form.
- 3) Clinically fit for an endoscopy.
- 4) One of the following options:
 - b) Previous confirmed diagnosis of Barrett's esophagus with intestinal metaplasia, and Prague classification of at least one circumferential centimeter of BE or a total BE segment length of at least 3 centimeters (C1+ or CXM3+) (BE arm). OR
 - c) If the subject does not have documented Prague Classification prior to screening, but the PI is convinced that the subject will meet the inclusion criteria based on previous documentation (for instance, mention of "long-segment BE," they may enroll the subject in the study at their discretion. The study upper endoscopy must confirm that the subject has C1+ or CXM3+ (BE arm). If (C1+ or CXM3+) is not observed at the time of study endoscopy, the subject may still be enrolled but not included in the data analysis with the BE cohort. The data may be analyzed in a separate cohort. OR
 - d) Self-reported heartburn or regurgitation on at least a monthly basis for at least 6 months (GERD arm).

